11.2 Data Analyses Plans

The primary analysis will report the count, proportion and corresponding 95% binomial confidence interval of evaluable patients who completed 4 cycles of pembrolizumab and at least one course of treatment of SBRT within 15 weeks from first dose of pembrolizumab.

The best overall response (CR + PR) by RECIST and Immune Related Response Criteria will be reported separately with counts, proportions and corresponding 95% binomial confidence intervals. Progression-free survival endpoints will be described with medians and Kaplan-Meier plots using product-limit estimates and associated 95% confidence intervals using RECIST and Immune Related Response Criteria separately. Frequency and severity of drug-related adverse events will be described. Each of the secondary endpoints will be described in the evaluable population and in the population who achieve treatment success as defined in the primary endpoint.

Correlative Analyses

PD-L1 expression on tumor cells and immune cells infiltrating tumor, and CIBERSORT/TIMER gene expression profiling correlatives will be analyzed with association to clinical outcomes using exact chi-square tests, t-tests, or Kaplan-Meier methods as is appropriate for each independent covariate and clinical outcome. Tumor mutational status and burden by tissue based next generation sequencing (MI-ONCOSEQ) results will be descriptive.

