8.1	Adverse Event Reporting Requirements	34
8.2	Definitions	35
8.3	Adverse Event Characteristics	36
8.4	Serious Adverse Event Reporting Guidelines	37
8.5	Routine Reporting	37
8.6	Reporting of Unanticipated Problems	37
9.0	DRUG INFORMATION	38
9.1	Pembrolizumab	38
10.0	CORRELATIVES/SPECIAL STUDIES	39
10.1	Sample Collection Guidelines	39
10.2	Specimen Banking	40
11.0	STATISTICAL CONSIDERATIONS	40
11.1	Study Design/Study Endpoints/ Sample Size & Accrual	40
11.2	Data Analyses Plans	41
12.0	DATA AND SAFETY MONITORING	41
13.0	REFERENCES	42

ABBREVIATIONS

AE	Adverse Event
ALT	Alanine Aminotransferase
ALC	Absolute Lymphocyte Count
Anti-PD(L)1	Anti-Programmed Death (Ligand) 1
AST	Aspartate Aminotransferase
BUN	Blood Urea Nitrogen
CBC	Complete Blood Count
CMP	Comprehensive Metabolic Panel
CR	Complete Response
CT	Computed Tomography
CTCAE	Common Terminology Criteria for Adverse Events
CTSU	Clinical Trials Support Unit
DLT	Dose Limiting Toxicity
DSMC	Data and Safety Monitoring Committee
H&P	History & Physical Exam
HRPP	Human Research Protections Program
IND	Investigational New Drug
IRB	Institutional Review Board
IV (or iv)	Intravenously
MTD	Maximum Tolerated Dose
NCI	National Cancer Institute
ORR	Overall Response Rate
OS	Overall Survival
PBMCs	Peripheral Blood Mononuclear Cells
PD	Progressive Disease
PFS	Progression Free Survival
PI	Principal Investigator
p.o.	per os/by mouth/orally
PR	Partial Response
PRC	Protocol Review Committee
SAE	Serious Adverse Event
SBRT	Stereotactic Body Radiation Therapy
SD	Stable Disease
SGOT	Serum Glutamic Oxaloacetic Transaminase
SPGT	Serum Glutamic Pyruvic Transaminase
UaP	Unanticipated Problem
UMCCC	University of Michigan Comprehensive Cancer Center
WBC	White Blood Cells

STUDY SCHEMA

SBRT and Anti-PD(L)1 Schedule

[figure not shown]

Figure 1: Study Schema. Abbreviations: Anti-PD(L)1=Pembrolizumab in this trial, Anti-PD(L)1 Cycle Length= 3 weeks *Imaging will occur at week 12 +/- 7 days

STUDY SYNOPSIS

Title	FAST: Feasibility trial of Anti-PD(L)1 and SBRT in the Treatment of Advanced, Platinum-Refractory Urothelial Carcinoma
Phase	Feasibility
Methodology	Single Arm
Study Duration	12 months treatment, up to 24 months follow-up
Study Center(s)	University of Michigan

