2.4 Endpoints

Primary Endpoint

1. Proportion of subjects who receive 4 doses of pembrolizumab and at least one session of treatment of SBRT within 15 weeks from the first dose of pembrolizumab.

Secondary Endpoints

1. Frequency and severity of Grade 3-5 drug-related adverse events graded by CTCAE v4.30.
2. Overall response proportion (Best Overall Response) and Progression Free Survival by RECIST, and Immune Related Response Criteria.

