5.2 Toxicities and Dosing Delays/Dose Modifications

Any patient who receives one dose of pembrolizumab will be evaluable for toxicity. Each patient will be assessed for the development of toxicity according to the Time and Events Table (Section 6.4). Toxicity will be assessed according to the NCI Common Terminology Criteria for Adverse Events (CTCAE), version 4.03. Dose adjustments should be made according to the system showing the greatest degree of toxicity.

Dose modifications in strength are not permitted for pembrolizumab

Dosing delays for Pembrolizumab:

- No dose delays for pembrolizumab are needed for hematologic changes.

- With any grade 2 or higher **non-hematologic toxicity deemed to be related to pembrolizumab**, hold pembrolizumab and refer to section 5.2.1. If adverse event is not an event of interest and improves to grade 1 or better, pembrolizumab may be resumed.
- If non-hematologic toxicity does not improve to grade 1 or better in 12 weeks from prior dose, discontinue pembrolizumab.

5.2.1 **Events of interest for Pembrolizumab:**

Certain adverse events that are possibly immune mediated warrant special monitoring and management, and are outline below to guide investigators.

5.2.1.1 **Pulmonary:**

Rule out non-inflammatory causes. If non-inflammatory cause, treat accordingly and continue protocol therapy. Evaluate with imaging and pulmonary consultation.

Grade of pneumonitis (NCI CTCAE v4.03)	Management	Follow-up
Grade 1 Radiographic Changes Only	
 • Consider delay of pembrolizumab • Monitor for symptoms every 2-3 days • Consider pulmonary and infectious disease consultations 	
 • Re-image at least every 3 weeks • If worsening, treat as grade 2, 3 or 4
Grade 2 Mild to moderate new symptoms	
 • Delay pembrolizumab • Consult pulmonary and infectious disease • Monitor symptoms daily, consider hospitalization • 1.0mg/kg/day methylprednisolone IV or oral equivalent • Consider bronchoscopy and/or lung biopsy 	
 • Re-image every 1-3 days • Consider prophylactic antibiotics while on steroids • If improves: 
 • When symptoms return to near baseline, taper steroids over at least one month • When steroids are at 10mg oral prednisone (or equivalent) or below, resume pembrolizumab • If not improving after 2 weeks or worsening, treat as grade 3 or 4

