5.2.1.8 Infusion Related Reactions

Pembrolizumab can cause severe or life-threatening infusion-related reactions, including hypersensitivity and anaphylaxis, which have been reported in 6 (0.2%) of 2799 patients receiving Pembrolizumab.

Monitor patients for signs and symptoms of infusion-related reactions including rigors, chills, wheezing, pruritus, flushing, rash, hypotension, hypoxemia, and fever.

For severe (Grade 3) or life-threatening (Grade 4) infusion-related reactions, stop infusion and permanently discontinue pembrolizumab

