5.6 Duration of Therapy

In the absence of treatment delays due to adverse events, treatment will continue for 17 cycles or until one of the following criteria apply:

- Disease progression as defined in Section 7.0
- Patients may continue on pembrolizumab beyond the first progression by imaging as long as investigator deemed clinical benefit continues
- Inter-current illness that prevents further administration of treatment
- Unacceptable adverse event(s) or death
- Patient voluntarily withdraws from treatment
- General or specific changes in the patient's condition render the patient unacceptable for further treatment in the judgment of the investigator

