Note: If subjects respond to treatment and are able to have their disease resected, the patient’s response will be assessed prior to the surgery.

Duration of Response

Duration of overall response: The duration of overall response is measured from the time measurement criteria are met for CR or PR (whichever is first recorded) until the first date that recurrent or progressive disease is objectively documented (taking as reference for progressive disease the smallest measurements recorded since the treatment started).

The duration of overall CR is measured from the time measurement criteria are first met for CR until the first date that recurrent disease is objectively documented.

Duration of stable disease: Stable disease is measured from the start of the treatment until the criteria for progression are met, taking as reference the smallest measurements recorded since the treatment started.

Progression-Free Survival

Progression-free survival (PFS) is defined as the duration of time from start of treatment to time of progression or death, whichever occurs first. Patients without progression or death will be censored at the date of their last scan.

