11.0 STATISTICAL CONSIDERATIONS

11.1 Study Design/Study Endpoints, Sample Size and Accrual

The primary aim of this study is to determine the feasibility of treating patients with metastatic urothelial carcinoma who have progressed after platinum based chemotherapy with sequential pembrolizumab and SBRT. Treatment success will be defined as completion of 4 cycles of pembrolizumab and at least one course of treatment of SBRT within 15 weeks from first dose of pembrolizumab. The trial will define the combination treatment as feasible if 70% of the patients receive the treatment as defined. With 20 evaluable patients, if 14 out of 20 (70% [95% Confidence Interval: 50% - 90%]) achieve successful treatment then the trial will conclude that further evaluation of sequential pembrolizumab and SBRT should be explored. A patient is evaluable for feasibility and safety if they receive at least one dose of pembrolizumab. Patients who achieve a complete response prior to SBRT are not evaluable for feasibility. Non-evaluable patients will be replaced. With accrual of 1-2 patients per month the trial accrual is expected to take up to 24 months.

Secondary endpoints will include efficacy and safety. Efficacy will be measured using the following endpoints: best overall response by RECIST and Immune Related Response Criteria and progression-free survival by RECIST and Immune Related Response Criteria. Safety endpoints will measure the frequency and severity of grade 3-5 drug-related adverse events of the combination of SBRT and pembrolizumab.

Correlative plans are described separately below.

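### Section 11.2 describes response, PFS and adverse events in a treatment-success group selected after baseline, with PFS timed from the start of treatment, and does not say which evaluable population is the denominator for response

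*Combined protocol and SAP*

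**What the plan says.** Section 11.2 states that each secondary endpoint will be described "in the evaluable population and in the population who achieve treatment success as defined in the primary endpoint". The secondary endpoints are best overall response and PFS, each by RECIST and by the immune-related criteria, and grade 3-5 drug-related adverse events (2.4, 11.1).

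Section 11.1 reads: "Treatment success will be defined as completion of 4 cycles of pembrolizumab and at least one course of treatment of SBRT within 15 weeks" of the first dose. Section 2.4 counts four doses and an SBRT session instead of four completed cycles and an SBRT course.

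Section 7.1 sets the time origin: "Progression-free survival (PFS) is defined as the duration of time from start of treatment to time of progression or death". Section 11.2 plans Kaplan-Meier curves and medians, and mentions no landmark and no caution for the success group.

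Two provisions limit how far early progression excludes a patient. Section 5.6 says "Patients may continue on pembrolizumab beyond the first progression by imaging as long as investigator deemed clinical benefit continues", and the study schema says "Imaging will occur at week 12 +/- 7 days", which is nominally after dose 4.

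The term evaluable has three definitions:
- **Safety** (5.10, 11.1): at least one dose of pembrolizumab.
- **Feasibility** (5.10, 11.1): the same, but without patients in complete response before SBRT, who are replaced.
- **Objective response** (7.1): measurable disease, at least one dose and a re-evaluation. Objective progression before the end of cycle 1 also qualifies.

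**The concern.** Membership of the success group is known only weeks after the PFS clock starts. A patient who dies or stops pembrolizumab before dose 4 cannot belong to it, so members carry about two months of guaranteed survival into their PFS. This is immortal-time bias.

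Response and adverse events are selected by the same later outcome. For adverse events the selection touches the endpoint itself. Section 2.4 defines that endpoint as "Frequency and severity of Grade 3-5 drug-related adverse events graded by CTCAE", while section 5.2.1.8 says for grade 3 or 4 "infusion-related reactions, stop infusion and permanently discontinue pembrolizumab", and the pneumonitis table in 5.2.1.1 also discontinues drug at grade 3 or 4. A patient with such an event before dose 4 leaves the group in which toxicity is described.

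The protocol cites a 21% response rate for pembrolizumab alone (1.1, 1.2) and names monotherapy as the reference therapy in its synopsis. A success-group response rate or PFS curve read beside that background could look like a benefit of SBRT when there is none. An unsettled response denominator adds a second way for the rate to move after the results are known.

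**Working it through.** **The plan's own figure.** For 14/20: 0.70 ± 1.96 × √(0.7 × 0.3/20) = 49.9% to 90.1%, matching the stated 50%-90%. It is not in dispute.

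**Timing.** With 21-day cycles (5.1.1), dose 4 falls 3 × 21 = 63 days after dose 1 (day 64), or 63/30.44 = 2.07 months. The window is 15 × 7 = 105 days.
- Success counted at dose 4: slack 105 − 63 = 42 days.
- Success counted at completion of cycle 4: slack 105 − 84 = 21 days.

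Section 5.2 says "If non-hematologic toxicity does not improve to grade 1 or better in 12 weeks from prior dose, discontinue pembrolizumab". A hold that long delays dosing by 84 − 21 = 63 days, more than either slack, so a long toxicity hold can also exclude a patient.

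**Response: a bound that needs no model.** With s successes of 20, responders among successes cannot outnumber responders overall. The success-group rate is therefore at most 20/s times the overall rate: 20/14 = 1.43, 20/16 = 1.25. The same holds for the proportion progression-free at any time if there is no censoring.

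Illustration with 4 responders and 14 successes (exact 95% intervals):
- All 20: 4/20 = 20.0% (5.7-43.7).
- All responders are successes: 4/14 = 28.6% (8.4-58.1).
- One responder is not a success: 3/14 = 21.4% (4.7-50.8).

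**PFS: assumption needed.** The documents give no median PFS. Assume exponential PFS with median m = 3 months, success share N, and every non-success having a PFS event before dose 4. After dose 4 the success-group curve is S(t)/N, with median −ln(0.5N) × m/ln 2.

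| Who is excluded | N | Success-group median (months) |
|---|---|---|
| Only deaths before dose 4, assumed 6.5% | 0.935 | 3.29 |
| Only deaths before dose 4, 13.0% | 0.870 | 3.60 |
| Share fixed at 14/20 | 0.70 | 4.54 |
| Every early progression or death | 0.620 | 5.07 |

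The 13.0% is 1 − 2^(−2.07/10.3), from the 10.3-month median survival in 1.2. The 0.620 is 2^(−2.07/3). At N = 0.70, the proportion progression-free reads 0.529/0.70 = 76% instead of 53% at week 12, and 0.279/0.70 = 40% instead of 28% at week 24. For scale, the sample median of 20 patients with a true median of 3 months has a 95% range of about 1.5 to 5.25 months.

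**Adverse events: both directions.** Suppose 3 of 20 patients have a grade 3-5 drug-related event: 15% (3.2-37.9). If two of them stopped before dose 4, the success group shows 1/14 = 7.1% (0.2-33.9). If all three are successes, it shows 3/14 = 21.4% (4.7-50.8).

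**Response denominator.**
- 7.1 set, 4 responders among 20 dosed: if 1, 3 or 5 patients are never re-evaluated, the rate becomes 4/19 = 21.1%, 4/17 = 23.5% (6.8-49.9) or 4/15 = 26.7%.
- Feasibility set: if 21 are dosed with 5 responders, one of them in complete response before SBRT, 5/21 = 23.8% becomes 4/20 = 20.0%.

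These are illustrations, not bounds.

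**The case against.** The strongest reply is that the analyses are descriptive, the success group is openly labelled by its rule, and the evaluable population is reported alongside. No comparison of successes with failures and no test against 21% is planned. All of that stands and limits the severity.

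The size of the PFS shift is also open to challenge. Early progression does not by itself exclude a patient, because treatment may continue past it and the first scheduled scan follows nominal dose 4. Non-success can also come from missed SBRT, delay or withdrawal, none of which is a PFS event. The 4.5-month figure is therefore close to an upper case, and with progression recorded only at 12-weekly scans the recorded median is unstable. This narrows the size. It does not remove the direction, because a death before dose 4 always excludes.

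A reader might infer that toxicity must look milder among successes. The documents do not fix that direction. The tables in 5.2.1 allow resumption after several grade 3 events, colitis among them. Successes receive at least four doses, and events are collected to 30 days after the last dose (8.1), so their exposure is longer.

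A reader might also infer that 11.2 names no set for response, or that response is necessarily overstated. Neither holds. The sentence covers every secondary endpoint, so response is assigned to the evaluable population; what is missing is which definition. Within section 11 the only definition is at least one dose, with the feasibility exclusion. On that reading, patients never re-evaluated are already in the denominator.

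**Conclusion.** The point stands at minor to moderate weight.

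Success-group PFS is biased upward by construction. Its size depends on assumptions: about 3.3 to 5.1 months for an assumed exponential median of 3 months, which is within sampling error at n = 20. In a single small sample, exclusions unrelated to prognosis could mask it. Success-group response can be raised by a factor of at most 20/s, and can also fall if responders stop early. Adverse events are selected with no determinate net direction.

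The response denominator is ambiguous rather than absent. The upward effect arises only under the 7.1 set. It is softened by the end-of-treatment tumor measurement (6.2) and by the instruction in 7.1 to document progression after discontinuation, but follow-up imaging stops at withdrawal of consent or new anti-cancer treatment (5.8). The downward effect under the feasibility set should be rare, since SBRT starts by cycle 2 and the first scheduled scan is at week 12.

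A reader might extend this to the feasibility conclusion. The documents do not support that: the 14/20 rule uses neither the success-group results nor the response set. Safety analysis in all dosed patients is already planned (7.3) and is not in question.

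**What to change.** 1. In 11.2, drop success-group PFS, which is simplest. Otherwise time it from a week-15 landmark among patients alive and progression-free then. By week 15 success status is known and the week-12 scan, with its window, is past.
2. Label success-group response and adverse-event results as exploratory and selected on a post-baseline outcome, and show them only beside the all-dosed results.
3. Report response in all patients with at least one dose, including those in complete response before SBRT, and count those not re-evaluated as non-responders. Amend 7.1 to match.
4. Reconcile the success definitions in 2.4 and 11.1 (doses or completed cycles; SBRT session or course), because they decide who is in the group.

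The cost is analysis wording and possibly slightly less favourable secondary figures. If the landmark is kept, its set is small. At 105/30.44 = 3.45 months, 20 × 2^(−3.45/m) gives about 6, 9 or 13 patients for assumed medians m of 2, 3 or 6 months, before splitting by success.

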While the tumor immune environment is often characterized by IHC analysis, it is also possible to evaluate the tumor immune environment with gene expression profiling. In a recent publication by Newman et al, they describe a technique called CIBERSORT (Cell-type Identification by Estimating Relative Subsets of RNA Transcripts) [19]. This is a technique that combines gene expression profiling with a complex computational method that can identify the relative fractions of immune cell subsets in tumor tissue. This technique correlated well with flow cytometry but has not been extensively evaluated clinically. It is possible this technique could be superior to standard evaluation by immunohistochemistry (IHC) due to the limited repertoire of phenotypic

markers used for classification of the immune infiltrate by IHC. As a subproject of OncoSeq analysis, we will analyze gene expression profiles using next generation sequencing based computational methods that accurately resolves relative fractions of various cell subsets using CIBERSORT/TIMER. We will obtain tumor tissue and explore an analysis of the tumor immune infiltrate by CIBERSORT. We will explore correlation between the CIBERSORT/TIMER data and clinical outcomes.

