2.3 Correlative Objectives

1. To determine PD-L1 expression on tumor cells and tumor immune infiltrating cells in archival tumor specimens and correlate these findings with clinical outcomes
2. To evaluate the tumor mutational profile and burden by tissue based next generation sequencing (MI-Oncoseq) of fresh and/or archival tissue and correlate with clinical outcomes.
3. To evaluate the tumor immune infiltrate of tumor tissue by gene expression profiling using CIBERSORT/TIMER and correlate these findings with clinical outcome.

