6.2 Time and Events Table

All assessments have a window of \pm 5 business days except for imaging/tumor measurements where a window of \pm 7 business days will apply.

Study Calendar

	Screening period (within 28 days)	C1 D1 ¹	SBRT (will commence no later than initiation of cycle 2) ³	C2 D1	C3 D1	C4 D1	Week 12	C5 D1	Cycles per std frequency for drug Every 12 weeks	End of Treatment	Follow-up (every 12 weeks for up to 24 months) ⁵
Informed Consent for FAST	X										
Informed Consent for MI-Oncoseq ⁴	X										
Archival Tissue identified	X										
Serum and Plasma banking	X ²										
Optional Biopsy at Progression										X	
History and Physical	X	X		X	X	X		X	X	X	
ECOG PS	X	X		X	X	X		X	X	X	
Tumor Measurements	X						X			X	X
Toxicity Evaluation	X	X		X	X	X		X	X	X	
CBC with diff and platelet count	X	X		X	X	X		X	X	X	
Comp metabolic panel	X	X		X	X	X		X	X	X	
Amylase/Lipase	X							X		X	
TSH, free T3, free T4 (IF clinically indicated: FSH, LH, ACTH)	X							X		X	
HIV, Hepatitis B Surface Antigen	X										
Pregnancy test for WOCBP	X										
CT Chest	X						X			X	X

CT or MRI Abdomen/Pelvis	X						X			X		X
Pembrolizumab		X		X	X	X		X	X			
SBRT			X									

¹Cycles are 21 days in duration.

² Serum and plasma banking will be collected C1D1 prior to first dose

³SBRT cannot overlap with C1D1

⁴Optional

⁵ Continue follow-up after end of treatment is for patients who discontinue study treatment for reasons other than progressive disease or death AND patients who continue on treatment past 17 cycles. These patients should continue to be followed by imaging every 12 weeks with standard of care CT chest, abdomen/pelvis until documentation of progressive disease, death, withdrawal of consent, or initiation of a new anti-cancer treatment for up to 2 years.

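### For continuous immune-cell fractions against PFS, Section 11.2 lists only Kaplan-Meier, which needs a cut-point the plan does not fix; an uncut Cox model would use the data better

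*Combined protocol and SAP*

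**What the plan says.** The third objective in Section 2.3 is "To evaluate the tumor immune infiltrate of tumor tissue by gene expression profiling using CIBERSORT/TIMER and correlate these findings with clinical outcome". Section 1.4 explains that the technique "can identify the relative fractions of immune cell subsets in tumor tissue", so each marker is a continuous fraction. The same section says the technique has had little clinical evaluation, and it gives no threshold.

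The first objective is "To determine PD-L1 expression on tumor cells and tumor immune infiltrating cells in archival tumor specimens and correlate these findings with clinical outcomes". Neither a scoring scale nor a cut-point is given for PD-L1.

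The analysis rule is one sentence in Section 11.2. It opens by naming the two marker families it covers: "PD-L1 expression on tumor cells and immune cells infiltrating tumor, and CIBERSORT/TIMER gene expression profiling correlatives will be analyzed with association to clinical outcomes". Its second half names the permitted tools, three in number: "using exact chi-square tests, t-tests, or Kaplan-Meier methods as is appropriate for each independent covariate and clinical outcome". Sequencing results for mutational status and burden are to be descriptive only, so they fall outside this point.

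PFS is a secondary endpoint in Section 2.4. Section 7.1 makes it a right-censored time: "Patients without progression or death will be censored at the date of their last scan".

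The Synopsis labels the correlative objectives exploratory. No significance level, effect size, event count or power is stated for them.

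**The concern.** Set the three listed methods against the types of data. The exact chi-square test relates a category to a category. The t-test relates a continuous marker to a two-group outcome such as response. Kaplan-Meier handles a censored time, but only by comparing groups of patients. None relates a continuous marker to a censored time on the marker's own scale, and the words on appropriateness choose among the three without adding a fourth. For CIBERSORT/TIMER fractions against PFS, the listed route is therefore to split each fraction into groups.

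Two things are at stake. With about 20 patients, a split throws away information on how far each patient lies from the cut. And because no cut is fixed, it can be settled once the curves are visible, separately for every cell subset. The same applies to PD-L1 if it is scored as a percentage.

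**Working it through.** **The plan's own figures.** No power is stated for the correlatives, so there is none to reproduce. The only computed design figure in the statistical section is "With 20 evaluable patients, if 14 out of 20 (70% [95% Confidence Interval: 50% - 90%]) achieve successful treatment". The simple normal interval gives 0.70 ± 1.96 × √(0.70 × 0.30 / 20) = 0.70 ± 0.20, or 49.9% to 90.1%, which matches. It matters here only because it sets N at 20.

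**Inputs from the documents.** N = 20 evaluable (11.1); continuous fractions (1.4); PFS censored at last scan (7.1). Marker numbers could be smaller: CIBERSORT is a subproject of the sequencing work (1.4), and in the study calendar (6.2) the row "Informed Consent for MI-Oncoseq" is footnoted as optional. No uptake is given.

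**Assumed inputs.** n = 15 as a lower figure; two-sided 5%; a normally distributed marker; a log-linear effect on the hazard; exponential PFS; a median-split log-rank test as the grouped comparator.

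**Analytic guide.** With D events and hazard ratio HR per SD, power is about Φ(√D × ln HR − 1.96) for the uncut marker and Φ(√(2D/π) × ln HR − 1.96) for a median split. The split thus acts as if only 2/π = 64% of the events had been seen.
- D = 15, HR 2: Φ(2.684 − 1.96) = 77% against Φ(2.142 − 1.96) = 57%, a loss of 19 points.
- D = 20, HR 1.5: Φ(1.813 − 1.96) = 44% against Φ(1.447 − 1.96) = 30%, a loss of 14 points.

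The approximation is rough with so few events, so simulation is the better guide.

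**Simulation.** 20,000 trials per row, no censoring, Cox likelihood-ratio test on the uncut marker against the log-rank test on a median split. Losses are taken before rounding.

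| n | HR per SD | Uncut | Split | Loss (points) |
|---|---|---|---|---|
| 15 | 1.2 | 10.6% | 10.2% | 0.5 |
| 15 | 1.5 | 27.3% | 20.4% | 7.0 |
| 15 | 2.0 | 57.5% | 39.8% | 17.8 |
| 15 | 2.5 | 76.6% | 55.2% | 21.4 |
| 20 | 1.2 | 12.0% | 10.3% | 1.7 |
| 20 | 1.5 | 36.1% | 25.2% | 10.8 |
| 20 | 2.0 | 71.9% | 51.0% | 20.8 |
| 20 | 2.5 | 88.8% | 68.8% | 20.0 |

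**Sensitivity.**
- Censoring: at 15%, the loss is 5.9 to 9.2 points at HR 1.5 and 16.0 to 22.6 at HR 2.0-2.5. At 30% it is 5.0 to 8.3 and 14.9 to 23.7.
- Scan dating: with PFS dated at 12-weekly scans (median PFS 16 weeks and censoring at 104 weeks, both assumed; 4,000 trials; score test), n = 20 and HR 2.0 give 68.6% against 48.4%. For n = 15 the figures are 54.1% against 36.7%, a loss of 17.4.
- Transformation: with exact dating in that same model, normal scores keep most of the gain. At n = 20 and HR 2.0, power is 69% for normal scores, 71% for the raw marker and 50% for the split.
- Shape: if the true effect is a threshold at the marker's population median, the order reverses. In one run of 6,000 trials, split against uncut was 43% against 39% (n = 20, HR 3), 58% against 51% (n = 20, HR 4) and 34% against 28% (n = 15, HR 3). A repeat with 20,000 trials put the reversal at about 5-6 points for HR 3 to 4.

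**The open cut.** For a marker with no effect (median PFS 16 weeks, 4,000 trials), a nominal 5% log-rank test rejects as follows:
- fixed median split: 6.8% (n = 15) and 6.1% (n = 20);
- best of the median and two tertile cuts: 16% and 14%;
- best cut within the central half of the data: 25% and 28%.

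These rates are per marker, before counting the number of cell subsets.

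**The case against.** The strongest reply is that there is no test here to lose power. The objectives are exploratory, the trial is a 20-patient feasibility study, and no log-rank test is named. Kaplan-Meier methods may mean curves and estimates, as they do for PFS elsewhere in 11.2. That stands, and it limits the importance of the point. It does not remove it: curves for a continuous fraction still need groups, and the cut is still open.

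A second reply is that log-linear data favour the Cox model by construction. This also stands; the threshold result belongs beside the gain, and the documents do not say which shape is likely.

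Third, the problem is narrow. For response, the t-test already uses the marker uncut. Section 1.4 frames the PD-L1 question around response, and its scale is unstated, so PD-L1 enters only conditionally. CIBERSORT/TIMER against PFS is the clear case. Clinical outcomes are not defined for the correlatives, although listing Kaplan-Meier implies a time-to-event outcome.

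A reader might infer three stronger things that the documents do not support:
- That a fixed loss of power follows from 15 to 20 patients. It does not; the loss is near zero at HR 1.2, and its sign depends on the shape of the effect.
- That the plan intends to search for a cut. It does not say so; it only fails to rule it out.
- That a Cox model cures multiplicity. One model per cell subset leaves the number of comparisons unchanged.

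**Conclusion.** The point holds in a limited form. For continuous CIBERSORT/TIMER fractions, and PD-L1 if scored as a percentage, the only method listed in 11.2 that copes with censored PFS requires a cut-point that the plan does not give.

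Under a normal marker, a log-linear effect, a median-split log-rank comparator and little censoring, at n = 15 to 20, the cost is about 0-2 points of power at HR 1.2 per SD, 7-11 at 1.5 and 17-23 at 2.0-2.5. A true threshold at the median turns this into an advantage of about 5-6 points for the split. The effect size, marker distribution, comparator, censoring rate and n = 15 are all assumptions.

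The primary feasibility conclusion, the response correlatives and the mutational analysis are untouched. This is an optional improvement to an exploratory analysis.

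**What to change.** Add to the correlative paragraph of 11.2: for PFS, continuous markers will be analysed uncut in single-covariate Cox models, using one transformation fixed in advance for all markers (for example normal scores). The hazard ratio per SD of the transformed marker will be reported with its 95% CI, labelled exploratory and unadjusted for the number of cell subsets. Kaplan-Meier curves split at the median will be shown for display only.

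Keep the exact chi-square test for markers that are categorical by assay, and the t-test for response.

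The transformation should be fixed now and not chosen if the data look skewed. That would only replace an open cut with an open transformation. An untransformed log-normal marker also raised the null rejection rate of the uncut test to 7.6-7.9%, against 6.4-6.7% for the split.

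The cost is two or three sentences, with no new data, patients or procedures. The downside is that a threshold effect would be detected slightly less well; the displayed curves would still help to show one.
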